**ABBREVIATIONS AND DEFINITIONS OF TERMS**

AYA	Adolescent and Young Adult
CRA	Clinical Research Associate
DFCI	Dana-Farber Cancer Institute
HRV	Heart Rate Variability
HRQOL	Health-Related Quality of Life
PRISM	Promoting Resilience in Stress Management
PRISM-AC	PRISM for Patients with Advanced Cancer
RCT	Randomized Controlled Trial
RPCA	Resilience in Pediatric Cancer Assessment
SCH	Seattle Children's Hospital

**1. Objectives**

**1.1 Overview.** Among patients with cancer and their families, early integration of palliative care may improve quality of life. This is particularly important for Adolescents and Young Adults (AYAs) because their distinct developmental challenges related to identity, relationships, and vocation may add to the burden of cancer. Among AYAs with advanced cancer, most understand that they may die and report that discussing end-of-life preferences, goals, and fears would be helpful; however, only 53% engage in such conversations. While national guidelines call for integrated palliative care in AYA oncology, developmentally targeted, evidence-based interventions designed to meet psychosocial and communication needs are lacking.

A potential barrier to improving the experiences of AYAs with advanced cancer may be their limited opportunities to develop “resilience resources” such as stress-management, goal-setting, positive reframing, and meaning-making skills. These resources may mitigate negative outcomes, facilitate engagement in goals of care discussions, and improve quality of life. Furthermore, promoting these resources among AYAs may give them the tools to more successfully navigate the challenges of the cancer experience.

Our research program is built on the central hypothesis that promoting resilience resources will improve psychosocial well-being. Over a series of studies, we developed a conceptual framework of resilience in pediatric cancer, affirmed associations between resilience resources and outcomes, and developed a novel resilience resources intervention (Promoting Resilience in Stress Management, PRISM). PRISM is a manualized, skills-based training program comprised of four 30-60 minute, in-person, one-on-one sessions plus a facilitated parent/caregiver/spouse/significant other family-meeting.

We recently completed a pilot Randomized Controlled Trial (RCT) to test the efficacy of PRISM among 100 AYAs, 6-months following their diagnosis of new (n=73) or recurrent (n=27) cancer (manuscript under review). Final results suggest PRISM is feasible, highly acceptable, and associated with increased patient-reported resilience as well as key clinically significant patient-centered outcomes such as quality of life and psychological distress. Subgroup analyses comparing patients with advanced cancer to those with new cancer suggested differentially stronger positive effects in the advanced cancer group, raising a hypothesis to be tested in dedicated trials. However, qualitative feedback from patients with advanced cancer suggested refinements targeting hopes, worries, and contextual meaning-making might strengthen PRISM’s usefulness.

**The overall objective of this project is to refine PRISM to meet the distinct needs of AYAs with Advanced Cancer. We will first adapt and iteratively test the existing PRISM based on established guidelines for intervention development. Then, we will conduct a multi-site randomized controlled trial to test the efficacy of a new PRISM for Advanced Cancer (PRISM-AC). Exploratory outcomes will assess a biomedical variable associated with psychological distress called heart rate variability (HRV). We hypothesize that AYAs with advanced cancer who receive PRISM will report fewer mixed affective symptoms and show improved biomedical outcomes. Findings will inform the development of larger dissemination studies and standards of AYA end-of-life and palliative care. Ultimately, this research has the potential to reduce the burden of cancer in a highly vulnerable population.**

## 1.2 Purpose of the Study Protocol

**1.2.1** The protocol is intended to be used by all study staff as the approved procedures for conduct of the study.

**1.2.2 Primary Aim:** Evaluate the effect of PRISM-AC compared to usual care on Health-Related Quality of Life (HRQOL) among AYAs with advanced cancer or recurrent/progressive tumors.

**1.2.2.1 Primary Outcome Measure:** AYA-reported Pediatric Quality of Life Inventory 4.0 (PedsQL) scores 3-months post-enrollment.

**1.2.2.2 Primary Hypothesis:** PRISM will be associated with higher patient-reported HRQOL compared to usual care.

### 1.2.3 Secondary Aims

**1.2.3.1 Create PRISM-AC by refining the existing PRISM for patients with advanced cancer.**

**1.2.3.1.1 Deliverable:** Refined manual of PRISM with targeted elements to meet the needs of patients with advanced cancer.

**1.2.3.1.2 Anticipated Findings:** PRISM-AC will target the same 4 resilience resources and have additional module and practice opportunities for meaning-making and advance care planning.

**1.2.3.2 Assess the feasibility and acceptability of PRISM-AC.**

**1.2.3.2.1 Deliverable:** feasibility will be defined as >70% enrollment and >70% completion of at least 4 sessions. Acceptability will be evaluated qualitatively.

**1.2.3.2.2 Anticipated Findings:** PRISM-AC will be feasible and acceptable.

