**Table 1. Original PRISM intervention content**

Topic	Details	Format
1. Managing Stress	Mindfulness techniques, relaxation strategies, obtaining social support	One-on-One
2. Goal-setting	Setting specific, realistic, desirable goals, planning for roadblocks	
3. Positive Reframing	Recognizing negative self-talk, replacing with positive, realistic, manageable ones	
4. Meaning Making	Identifying benefits, purpose, meaning, or legacy from cancer experience	
5. Coming Together	Discussion about what was learned, what helped, what they can do to help	Family meeting
6. Boosters	In-person/digital/video conference modules to practice, further develop, and track skills.	One-on-One
7. Practice Opportunities	Paper-pencil and app-based modules to practice and further develop skills	Digital or Paper

Note: Sessions delivered approximately every 1-2 weeks, arranged in advance in conjunction with clinic and hospital visits.

**2.1.2.5 Feasibility and Acceptability study of PRISM Intervention.** We completed a formative study of PRISM among 24 AYAs to determine the optimal content and timing of PRISM sessions. We found it to be feasible and highly valuable to AYA patients and parents. Eighty percent of AYA participants completed the intervention and feedback was universally positive: "This was so helpful, I wish we had done this sooner," or "I think it's good techniques to use, definitely. I am teaching my little sister. I'm sure it can help her, too."

[figure not shown]
**2.1.2.6 PRISM Phase II RCT (clinicaltrials.gov NCT 02340884).** Next, in a phase II RCT testing PRISM efficacy among AYAs with new or recurrent cancer, we refined processes of enrollment, randomization, implementation, and data collection. We completed our target enrollment of 100 AYAs with either new or newly

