## 11.0 Data Analysis/Management

**11.1 Run-In Cohort:** Data will be analyzed descriptively, including demographic and clinical characteristics of participants (i.e., age, sex, cancer or tumor-type, time since diagnosis, number of days in hospital during PRISM study). Eligible AYAs who decline to participate will be asked to provide a reason for declining the study and the above characteristics will be obtained from the medical record; such that we can compare participants and non-participants to determine biases in enrollment preferences.

**11.2 “Feasibility”** will be defined as: (1) at least 70% enrollment of approached and eligible patients; and (2) at least 70% completion of the 5 main PRISM sessions (not including “Coming

Together,” as we have done for prior feasibility determinations) among enrolled patients. “Acceptability” will be assessed qualitatively, as we have done in all prior pilot studies of PRISM’s development. Briefly, prior to each session (beginning with session #2), interventionists will solicit feedback regarding the usage and utility of the prior learned skill(s). Following the final session, we will solicit more detailed feedback regarding timing and value of the intervention and its content (see PRISM manual and Voicing My Choices session in appendices). Because the additional session involving early advance care planning is new for this study, we have designed additional pointed questions to gather user feedback about these exercises, including their perceived value, format preferences, timing, and if/how the session compares to the other skills (See Voicing My Choices appendix document). Finally, baseline and follow-up RPCA scores will be determined and these data will be entered into the secure database. For this pilot study, we will describe pre-and post-intervention scores and score changes for each instrument, with effect sizes calculated accordingly.

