**11.5.3.4 Additional analyses** will include process evaluations that include: (a) intervention fidelity; (b) satisfaction queries; and (c) mediation analyses to evaluate relationships between PRISM, family activation, and outcomes. For example, the intervention effect on parent outcomes may be mediated by parent activation. If we find a positive intervention effect on parent psychological distress, we will explore activation mediation using the counterfactual framework with indirect mediation effects computed through G-estimation and incorporating confounders of the mediator-outcome association. Finally, we will conduct a planned interim analysis for data-safety monitoring purposes when half of AYA participants have reached the primary endpoint (see Human Subjects).

**11.5.3.5 Multiple comparisons.** Multiple comparisons are a concern since we are collecting multiple measures from both patients and caregivers and are interested in several hypotheses. We minimize this problem by specifying a limited number of main hypotheses for each aim. False Discovery Rate criterion will be used to correct for multiple testing in analyses that are not pre-specified. Likewise, in manuscripts and presentations, we will report the number of tests performed and interpret results within this context.

**11.5.3.6 Considerations regarding missing data.** Effective data collection at scheduled times will be monitored and attrition minimized as described below. While our goal will be to minimize missing data, data may still be missing due to patients/families skipping individual items, omissions in medical records, lack of follow-up, medical complications, or death. We will quantify the amount of missing data, evaluate the association of participant characteristics with missing data, and minimize bias and increase efficiency in the associations of interest by applying appropriate methods to account for missing data. For example, where missing at random (MAR) is a plausible assumption, we will use multiple imputation or inverse probability weighting, depending on the statistical model being considered. For missing not at random (MNAR), we will use sensitivity analyses. In all cases, we will assess the robustness of estimates due to assumptions.

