
#### **14.2 Early Withdrawal of Subjects**

All participants may choose to withdraw from the study at any time. We will track date of discontinuation and request a brief reason to be recorded for tracking purposes. In the event of serious medical complications (or death) precluding participation, participants will be censored after 2 months of missing data. In all other cases, staff will continue to request surveys until 2 months following the study endpoint (12 months for RCT, 3 months for Run-In), as described above.

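### Acceptability of PRISM-AC is assessed from feedback tied to continued attendance, so the views of patients who stop sessions are not built in and the result may be optimistic

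*Combined protocol and SAP*

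**What the plan says.** Acceptability is part of a secondary aim. Section 1.2.3.2.1 gives feasibility numerical limits but says of acceptability only "Acceptability will be evaluated qualitatively". Section 11.2 repeats that it "will be assessed qualitatively, as we have done in all prior pilot studies" and is the only place where the method is set out. It names three sources:

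- Between sessions: "prior to each session (beginning with session #2), interventionists will solicit feedback regarding the usage and utility of the prior learned skill(s".
- At the end: "Following the final session, we will solicit more detailed feedback regarding timing and value of the intervention and its content". The person asking is not identified.
- On the new advance care planning session: "we have designed additional pointed questions to gather user feedback about these exercises". Their timing is in the Voicing My Choices appendix, which is not among the documents available here.

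Three other provisions touch on patients' opinions. Section 14.2, on early withdrawal, states: "We will track date of discontinuation and request a brief reason to be recorded for tracking purposes". Section 11.5.3.4, in the RCT analysis plan, lists "process evaluations that include: (a) intervention fidelity; (b) satisfaction queries" without saying who is asked or when. Section 13.6.3 has safety monitoring look at satisfaction with the intervention and at all complaints. None of the three is said to feed the acceptability assessment.

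Run-in surveys are collected at baseline, week 6 and week 12 (Section 9.3.1). The run-in instruments marked in Table 5 include none about PRISM-AC.

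**The concern.** The run-in exists to refine how the added fifth session is delivered before the RCT starts (Section 4.1). For that purpose the most informative opinions are those of patients who found a session unhelpful or upsetting, and such patients are among those who might not come back. A method that asks about each session at the next one, and for an overall view at the last, hears least from them. If some do stop for that reason, the acceptability account would look better than the experience of the whole enrolled group, and content that some patients rejected could pass into the RCT unchanged.

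Session 5 is the most exposed. It is the last of the main sessions. The session after it, Coming Together, can be declined by the patient or skipped if caregivers decline (Section 9.4), and it does not count towards completion (Section 11.2). A patient can therefore count as a completer without a clearly stated point at which session 5 is discussed.

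**Working it through.** The plan states no acceptability figure, so there is none to reproduce. The check has two parts.

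**1. What is heard, by stopping point, under Section 11.2 as described**

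- Stops after session 1: no session feedback, no final feedback.
- Stops after session k, for k = 2, 3 or 4: feedback on sessions 1 to k − 1, none on session k, no final feedback.
- Completes session 5 but not Coming Together: feedback on sessions 1 to 4. Feedback on session 5 depends on two things that the text leaves open: whether the final session means session 5 or Coming Together (Section 9.4 uses the term for the latter), and whether the appendix questions are asked within session 5.
- Attends everything: feedback on every session and at the end.

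The other routes do not fill the gaps:

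- Section 14.2 concerns withdrawal from the study, and the reason is recorded for tracking. It does not clearly cover someone who stops sessions but stays in the study.
- The satisfaction queries of Section 11.5.3.4 belong to the RCT analyses, after the run-in.
- Complaint monitoring depends on a patient volunteering a complaint.
- In Table 5, the Quality of Care checklist is about the care team (Section 9.6.1.1.8), and the satisfaction items in the Survey about Caring for Children with Cancer are about overall care (Section 9.6.1.3.2).

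The week-12 survey does not depend on session attendance, so it could reach patients who have stopped.

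**2. How many patients this could involve**

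Inputs: up to 30 run-in patients (Section 4.1); a 70% completion limit for the five main sessions (Section 11.2); in phase II, 49 assigned to PRISM, 48 with at least one session, 43 with all, and 2 on PRISM who declined to continue because of burden (Section 2.1.2.6). I use the Section 11.2 definition of completion; Section 1.2.3.2.1 counts at least four sessions.

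Patients without final feedback = 30 × (1 − completion rate), assuming that everyone who completes gives it:

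- At the 70% limit: 30 × 0.30 = 9.
- At the 80% completion of the formative study (Section 2.1.2.5): 30 × 0.20 = 6.
- At the phase II rate of 43/49 = 87.8%: 30 × 6/49 = 3.7, about 4.

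The 6 phase II non-completers comprise 49 − 48 = 1 who attended nothing and 48 − 43 = 5 who attended some sessions.

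The phase II rate of leaving because of burden was 2/49 = 4.1%. Applied to 30 patients, as an assumption, that is 30 × 2/49 = 1.2, about 1 patient. It comes from PRISM before the advance care planning session was added (Section 2.1.2.7), so it does not bound how many might stop because of session 5.

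**The case against.** The strongest reply is that patients who stop are not silenced. Anyone who stops after session 2 or later has already commented on earlier skills. Withdrawal reasons are requested, complaints are monitored and satisfaction queries are planned. Patients who opt out of Coming Together are still followed and offered a booster session (Section 9.4). The extra session 5 questions may be put during session 5 itself, in which case a patient put off by it is heard. Non-completion is not hidden either, since it is counted over enrolled patients under feasibility. Phase II attrition was mainly medical. The same style of feedback in phase II produced requests for change, including the new module (Section 2.1.2.7), so it can elicit criticism.

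Most of this stands, and it rules out several stronger readings that a reader might infer:

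- That those who disliked PRISM-AC are never heard. The routes above contradict this.
- That all feedback goes to the interventionist. Section 11.2 says so only for the between-session questions.
- That the formative study already shows the bias, because "Eighty percent of AYA participants completed the intervention and feedback was universally positive". Section 2.1.2.5 does not say why the others stopped or whether they were asked.

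What the reply does not supply is a link. No text says that withdrawal reasons, satisfaction queries or non-completers' views enter the acceptability assessment, and the booster prompts in Section 9.4 ask which skill to practise, not what the patient thought of it.

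**Conclusion.** The point holds as a gap in the acceptability method. Followed as written, Section 11.2 draws mainly on patients who keep attending, and the result may be optimistic, including for session 5. Neither the size nor the direction of any error is established. If those who stop do so for medical reasons and think of the sessions much as the others do, there is little or none.

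The count without final feedback, among 30, is 9 at the completion limit and about 4 at the phase II rate. These are patients not asked, not patients who disapprove. A reader might turn the first figure into 100% approval among the 21 completers against 70% (21/30) of all enrolled. The documents do not support that: acceptability is qualitative, no percentage is planned, and the 70% treats all nine as disapproving. Nor do they support saying that acceptability is overstated.

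The conclusion rests on Section 11.2 being the full method apart from the appendix. If the appendix places the session 5 questions within session 5, the gap for that session narrows to patients who leave before it or before the questions are put. The point affects one element of a secondary aim, not the primary RCT analysis. It is worth acting on because the remedy is cheap.

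**What to change.** Add the existing feedback questions, including those on session 5, to the week-12 run-in survey as a few self-completed items. Offer them to every enrolled patient regardless of sessions attended, with an answer option for not having attended or having stopped, and the reason.

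In Section 11.2, state that these answers and the discontinuation reasons from Section 14.2 are analysed together with the in-session qualitative feedback, which stays as planned. Report the number of non-completers, and the number who did not answer, beside the findings.

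The cost is a slightly longer week-12 survey for patients who may be ill. Some of those who stopped will still not reply, so the gap will be smaller and visible but not closed.

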**1.2.3.3 Determine if PRISM-AC improves other key patient-reported outcomes**

**1.2.3.3.1 Outcome Measures:** Anxiety and Depression (measured with Hospital Anxiety and Depression Scale, HADS), symptom burden (Memorial Symptom Assessment Scale, MSAS), hopeful patterns of thought (Hope Scale), Cancer-Specific Quality of Life (PedsQL 3.0 Cancer Module), and Resilience (Connor Davidson Resilience Scale, CDRISC-2) 3-months post-enrollment.

**1.2.3.3.2 Hypotheses:** PRISM recipients will report lower anxiety and depression, lower symptom distress, higher hope, and higher resilience compared to controls.

**1.2.3.4 Evaluate the impact of PRISM-AC on parent distress.**

**1.2.3.4.1 Outcome Measures:** parent anxiety (Generalized Anxiety Disorder Screener, GAD-7), depression (PHQ-8), and HRQOL (SF-36), 3-months post-enrollment.

**1.2.3.4.2 Hypothesis:** Parents of PRISM-AYAs will report lower anxiety and depression, and better HRQOL compared to parents of AYAs in usual care.

**1.2.3.4.3 Exploratory Outcome:** Family Experience (selected items from Hospital Consumer Assessment of Healthcare Providers and Systems [HCAHPS] survey).

**1.2.3.5** Evaluate the impact of PRISM-AC on family “palliative care activation.”

**1.2.3.5.1 Outcome measures:** (a) AYA- and parent- perceptions of AYA involvement in Decision-Making, measured with the Decision-Making Involvement Scale; (b) medical record documented goals of care conversations; and, (c) medical record documented AYA utilization of formal palliative care and other psychosocial services, hospice, limitation of intervention orders, and other advance care plans.

**1.2.3.5.2 Hypothesis:** PRISM families will demonstrate higher levels of activation compared to usual care.

**1.2.3.6** Explore longitudinal impact of PRISM-AC on above outcomes at 6-, 9-, and 12-months following enrollment.

#### **1.2.4 Exploratory Aims**

**1.2.4.1** Prospectively describe associations between PRISM, patient reported anxiety and depression, and stress biomarkers.

**1.2.4.1.1 Outcome measures:** heart rate variability (HRV) as measured by the standard deviation of normal to normal beats (SDNN).

**1.2.4.1.2 Hypothesis:** PRISM recipients will demonstrate larger improvements in HRV compared to controls.

### **1.3 Rationale for the Selection of Outcome Measures**

Palliative Care interventions aim to alleviate suffering and improve HRQOL. Hence, we selected HRQOL as our primary outcome, with additional clinically relevant patient-centered outcomes including symptom burden and psychological symptoms as our secondary outcomes.

Patient outcomes are not the only ones of import in pediatric, adolescent, and young adult populations. Indeed, patient and parent outcomes are inextricably linked. Parent psychological distress is highly prevalent among children with advanced cancer, and it is associated with perceived child suffering and quality of family communication. Hence, we elected to determine if a patient-centered intervention could also improve parent outcomes.

Regarding palliative care utilization, traditional measures focus on the circumstances of death (e.g., chemotherapy within the last 30 days, advance care planning documentation). These metrics are less relevant in pediatric and AYA populations. AYA advanced cancer may last years. Content and AYA participation in goals of care discussions evolve. Low-intensity palliative chemotherapy may improve quality of life. And, AYAs defer to their parents for medical decision-making, suggesting formal advance care planning documents incompletely represent AYA perspectives. For these reasons, pediatric palliative care research has shifted towards outcomes of patient/family engagement and activation. Activation is defined as the extension of self-efficacy into self-management. It implies knowledge and confidence to take action, actively change behaviors, and maintain changes over time. It may be more representative of evolving pediatric and AYA palliative care involvement. Importantly, higher activation is associated with improved psychological wellbeing and HRQOL among adults with chronic illness, and with medication-adherence and clinical outcomes in pediatric settings. Hence, we selected global activation as a measure of palliative care utilization in this study.

Emerging data indicate anxiety and depression can impact cancer-related outcomes through immune-mediated processes, with sympathetic nervous system activation as a central mechanism. HRV is a commonly used, noninvasive indicator of autonomic nervous system activity with published normative values.

Finally, few palliative care studies include longitudinal outcomes assessments. In order to explore the durable impacts of PRISM-AC, as well as capture cohort data to describe ongoing patient-reported and parent-reported outcomes, we will continue to survey patients and families quarterly for a year following their enrollment.

